Title Page

Title	A Prospective , Mono-Country, Multi-Center Study to observe the frequency of Extra-Axial symptoms in Korean Ankylosing Spondylitis patients on adalimumab therapy
Protocol Version Identifier	Version 2.0
Date of Last Version of Protocol	06 March, 2015
Marketing Authorisation Holder(s)	AbbVie Korea
Research Question and Objectives	
What is the frequency of EAMs in Korean AS patients and the effectiveness of adalimumab on EAMs?
 
Primary Objective
 
To investigate the frequency of EAMs in AS patients on adalimumab therapy in routine clinical practice
 
Secondary Objectives
 
• To observe the effectiveness of adalimumab on AS spinal disease activity in routine clinical practice• To investigate the effectiveness of adalimumab on EAMs in routine clinical practice
Country(-ies) of Study	South Korea
Author	

This study will be conducted in compliance with this protocol.

Confidential Information

No use or disclosure outside AbbVie is permitted without prior written authorization from AbbVie.

Adalimumab
P15-238 Protocol
Version 2.0

Marketing Authorisation Holder(s)

Marketing Authorisation Holder(s)	AbbVie Korea [Redacted]
-----------------------------------	----------------------------

2.0 Abbreviations

AE	Adverse Event
ADR	Adverse Drug Reaction
CRA	Clinical Research Associate
CRF	Case Report Form
EAM	Extra-Axial Manifestations
AS	Ankylosing Spondylitis
SAE	Serious Adverse Event
IBD	Inflammatory Bowel Disease
NSAID	Non-steroidal Anti-inflammatory drug
DMARDs	Disease Modifying Anti Rheumatic Drugs
BASDAI	Bath Ankylosing Spondylitis Disease Activity Index
MASES	Maastricht Ankylosing Spondylitis Enthesitis Score
TJC	Tender Joint Counts
SJC	Swollen Joint Counts
TNF	Tumor Necrosis Factor

4.0 Abstract

Title:

A Prospective, Mono-Country, Multi-Center Study to observe the frequency of Extra-Axial symptoms in Korean Ankylosing Spondylitis patients on adalimumab therapy

Rationale and Background:

In addition to chronic inflammation of the spine, extra-axial manifestations are common features in patients with ankylosing spondylitis (AS). Although AS is primarily a disease of the axial skeleton, peripheral joint involvement occurs in up to 70% of the patients⁽¹⁾. An epidemiological study of 847 patients in Belgium who fulfilled the modified New York criteria for AS found that 42% had one or more extra-articular manifestations, including acute anterior uveitis (27%), IBD (10%) and psoriasis (11%)⁽²⁾. According to a cross-sectional study in Korea of 830 AS patients⁽³⁾, three hundred and ninety-one patients (47.1%) were found to have a history of peripheral arthritis and six hundred and four patients (73.9%) were found to have a history of hip joint involvement. In same study, three hundred and forty-four patients (42.7%) were found to have enthesitis, which was the most common extra-articular symptom and also two hundred and forty-six patients (29.7%) were found to have a history of uveitis.

In a large cohort of patients with active AS, adalimumab effectively reduced enthesitis and peripheral arthritis^{(11),(12)}.

A single center, cross-sectional study⁽³⁾ revealed that Korean patients with AS have a higher frequency of peripheral arthritis and hip joint involvement. Though the frequency of peripheral arthritis was higher than reported results in Western countries⁽¹⁴⁾, epidemiological data on extra-axial manifestations in Korean AS patients are poor. Adalimumab is approved for immune mediated inflammatory diseases such as rheumatoid arthritis, ankylosing spondylitis, psoriatic arthritis, inflammatory bowel disease and psoriasis in Korea. There is currently no data on the effectiveness of adalimumab in extra-axial symptoms like peripheral arthritis, enthesitis or dactylitis in Korean AS patients.

This study will be the first prospective study of the frequency of EAMs in Korean AS patients being treated with adalimumab in routine clinical practice. .

Research Question and Objectives:

What is the frequency of EAMs in Korean AS patients and the effectiveness of adalimumab on EAMs?

Primary Objective

To investigate the frequency of EAMs in AS patients on adalimumab therapy in routine clinical practice

Secondary Objectives

- To observe the effectiveness of adalimumab on AS spinal disease activity in routine clinical practice
- To investigate the effectiveness of adalimumab on EAMs in routine clinical practice

Study Design:

This is a prospective, mono-country, multi-center study in AS patients treated with adalimumab. At least 200 subjects will be enrolled at approximately 10 sites.

The baseline assessment should be performed prior to the first dose of adalimumab (Visit1). Study visits will be conducted at 12, 28, 36 and 52 week after baseline. All subjects will have one Follow-up approximately 30days after the last dose of adalimumab.

The prescription of adalimumab is at the discretion of the physician in accordance with clinical practice and label, is made independently from this study and precedes the decision to offer the patient the opportunity to participate in this study.

Primary Endpoint:

The frequency of EAMs of interest at baseline: peripheral arthritis, enthesitis and dactylitis

Secondary Endpoints:

- The percentage of patients with 50% improvement of baseline BASDAI (BASDAI 50) at week 12, 28, 36, and 52
- The change of MASES (Maastricht Ankylosing Spondylitis Enthesitis Score) from baseline to week 12, 28, 36, and 52 in patients who had enthesitis at baseline
- The percentage of patients who have enthesitis of the plantar fascia from baseline to week 12, 28, 36 and 52.
- The change of dactylitis score from baseline to week 12, 28, 36 and 52 in patients who had dactylitis at baseline.
- The change of tender and swollen joint counts (TJC, 0-46; SJC, 0-44) from baseline to week 12, 28, 36 and 52 in patients who had peripheral arthritis (≥ 1 swollen joint) at baseline.

Population:

Subject will be adults with AS who meet the eligibility criteria.

Inclusion Criteria

- Subject must be an adult ≥ 19 years
- Subject has been diagnosed with ankylosing spondylitis according to the 1984 modified New York criteria for at least 3months
- Subject has active disease defined by a BASDAI score ≥ 4 despite treatment with at least 2 NSAIDs based on Korea AS reimbursement guideline.
- Subject is eligible for adalimumab in daily rheumatologic practice
- Subject must provide written authorization form to use personal and/or health data prior to the entry into the study.

Exclusion Criteria

- Female subjects who are pregnant or breast feeding


• Subject applies contraindication to any anti-TNF agent• Subject is participating in other clinical trials
Variables: 
• Demographics: Age, Gender, Family History of AS, Co-morbidity• Previous AS-related medication (medication, dosage)• Concomitant medication• BASDAI 50• Extra-axial symptoms: Enthesitis, Peripheral arthritis and Dactylitis (presence or absence)• Extra-axial symptoms assessment: MASES, enthesitis of the plantar fascia, TJC and SJC, Counts of dactylitic digits• Adalimumab administration• Extra-axial symptoms excluding Enthesitis, Peripheral arthritis and Dactylitis (If applicable, such as IBD, uveitis, etc.)
Data Sources: 
The investigator should maintain source documents for each subject in the study, consisting of medical records containing demographic data, and other information to be collected.

Study Size: 
The primary end point of this study is to investigate the frequency of extra-axial symptoms such as peripheral arthritis, enthesitis and dactylitis in eligible Korean AS patients.
 
With reference to a study in Korean AS patients^{(1),(3)}, peripheral arthritis, enthesitis and dactylitis were found in 70%, 53% and 1% in AS patients, respectively. We calculated sample size based on the expected frequency of peripheral arthritis and enthesitis.
 
By assuming 95% confidence interval and 15% confidence interval width, the sample size is estimated at 144 and 171 for peripheral arthritis and enthesitis, respectively. Considering 20% of drop-out rate, about 200 patients will be recruited.

Data Analysis: 
The study population will be classified by ITT (Intention-To-Treat) set and PP (Per-Protocol) set.
 
- ITT set: The ITT set will consist of those patients who have received at least one adalimumab treatment and have assessed EAMs at baseline.- PP set: The PP set will consist of those patients who meet inclusion/exclusion criteria and complete the study without any major protocol deviation of the patients included in the ITT set. 
General Considerations
 
Continuous variables will be described with the number of patients, arithmetic mean, standard deviation, median, minimum, and maximum. For categorical variables, the frequency and proportion will be presented. The values such as arithmetic mean, standard deviation, and proportion will be rounded to

two decimal places. If the observation value is missing value, it will be treated as a missing value in the analysis.

Baseline Characteristics including demographics

Descriptive statistics will be used to present variables regarding demographics and disease/medication related data. Continuous variables will be described with the number of patients, arithmetic mean, standard deviation, median, minimum and maximum. For categorical variables, the frequency and proportion will be presented. The values such as arithmetic mean, standard deviation, and proportion will be rounded to two decimal places.

If the observation value is missing value, it will be treated as a missing value in the analysis. Statistical analyses will be performed using SAS V9.2 or higher.

Milestones: Start of Data Collection: 4Q 2014

End of Data Collection: 1Q 2017

Final Report of Study Results: 4Q 2017

5.0 Amendments and Updates

NA

6.0 Milestones

Major study milestones and their planned dates are as follows:

Start of Data Collection:	4Q 2014
End of Data Collection:	1Q 2017
Final Report of Study Results:	4Q 2017

7.0 Rationale and Background

7.1 Introduction

In addition to chronic inflammation of the spine, extra-axial manifestations are common features in patients with ankylosing spondylitis (AS). Although AS is primarily a disease of the axial skeleton, peripheral joint involvement occurs in up to 70% of the patients⁽¹⁾. An epidemiological study of 847 patients in Belgium who fulfilled the modified New York criteria for AS found that 42% had one or more extra-articular manifestations, including acute anterior uveitis (27%), IBD (10%) and psoriasis (11%)⁽²⁾. According to a cross-sectional study in Korea of 830 AS patients⁽³⁾, three hundred and ninety-one patients (47.1%) were found to have a history of peripheral arthritis and six hundred and four patients (73.9%) were found to have a history of hip joint involvement. In same study, three hundred and forty-four patients (42.7%) were found to have enthesitis, which was the most common extra-articular symptom and also two hundred and forty-six patients (29.7%) were found to have a history of uveitis.

Non-steroidal anti-inflammatory drugs (NSAIDs) remain first-line agents for the treatment of AS⁽⁴⁾. Disease-modifying anti-rheumatic drugs (DMARDs) do not have a satisfactory effect on axial disease. Sulfasalazine has some effect on extra-axial arthritis⁽⁵⁾ but its benefit for treating enthesitis does not outweigh its risks⁽⁴⁾. Tumor necrosis factor

(TNF) antagonists, including the monoclonal antibodies adalimumab, infliximab and the TNF-receptor construct etanercept are highly effective agents for the treatment of patients who still have active AS despite the treatment with NSAID⁽⁵⁾⁻⁽¹⁰⁾. In a large cohort of patients with active AS, adalimumab effectively reduced enthesitis and peripheral arthritis^{(11),(12)}. Most clinicians understand that the presence of comorbid conditions reduces the quality of life (QoL) of patients. Two patients with the same degree of back pain and radiographic findings will not have the same QoL if one of them also has psoriasis, for example. The presence of comorbidities is a significant determinant of the mental health-related impact of AS on QoL⁽¹³⁾; therefore, it is important to screen for extra-articular manifestations and comorbid conditions in patients diagnosed with AS.

7.2 Rationale

A single center, cross-sectional study⁽³⁾ revealed that Korean patients with AS have a higher frequency of peripheral arthritis and hip joint involvement. Though the frequency of peripheral arthritis was higher than reported results in Western countries⁽¹⁴⁾, epidemiological data on extra-axial manifestations in Korean AS patients are poor. Adalimumab is approved for immune mediated inflammatory diseases such as rheumatoid arthritis, ankylosing spondylitis, psoriatic arthritis, inflammatory bowel disease and psoriasis in Korea. There is currently no data on the effectiveness of adalimumab in extra-axial symptoms like peripheral arthritis, enthesitis or dactylitis in Korean AS patients.

This study will be the first prospective study of the frequency of EAMs in Korean AS patients being treated with adalimumab in routine clinical practice.

8.0 Research Question and Objectives

What is the frequency of EAMs in Korean AS patients and the effectiveness of adalimumab on EAMs?

Primary Objective:

To investigate the frequency of EAMs in AS patients on adalimumab therapy in routine clinical practice

Secondary Objectives:

- To observe the effectiveness of adalimumab on AS spinal disease activity in routine clinical practice
- To investigate the effectiveness of adalimumab on EAMs in routine clinical practice

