9.0 Research Methods

9.1 Study Design

This is a prospective, mono-country, multi-center study in AS patients treated with adalimumab.

At least 200 subjects will be enrolled at approximately 10 sites.

Physicians will be asked to document on a separate log the number of patients who are possible to participate in this study. Presence or absence of EAMs and decision to participate will be collected.

The baseline assessment should be performed prior to the first dose of adalimumab (Visit1). Study visits will be conducted at 12, 28, 36 and 52 week after baseline. All subjects will have one Follow-up approximately 30days after the last dose of adalimumab.

Primary Endpoint:

- The frequency of EAMs of interest at baseline: peripheral arthritis, enthesitis and dactylitis

Secondary Endpoints:

- The percentage of patients with 50% improvement of baseline BASDAI (BASDAI 50) at week 12, 28, 36, and 52
- The change of MASES (Maastricht Ankylosing Spondylitis Enthesitis Score) from baseline to week 12, 28, 36, and 52 in patients who had enthesitis at baseline
- The percentage of patients who have enthesitis of the plantar fascia from baseline to week 12, 28, 36 and 52.
- The change of dactylitis score from baseline to week 12, 28, 36 and 52 in patients who had dactylitis at baseline.
- The change of tender and swollen joint counts (TJC, 0-46; SJC, 0-44) from baseline to week 12, 28, 36 and 52 in patients who had peripheral arthritis (≥ 1 swollen joint) at baseline.

The prescription of adalimumab is at the discretion of the physician in accordance with clinical practice and label, is made independently from this study and precedes the decision to offer the patient the opportunity to participate in this study.

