9.7 Data Analysis

The study population will be classified by ITT (Intention-To-Treat) set and PP (Per-Protocol) set.

- ITT set: The ITT set will consist of those patients who have received at least one adalimumab treatment and have assessed EAMs at baseline.

- PP set: The PP set will consist of those patients who meet inclusion/exclusion criteria and complete the study without any major protocol deviation of the patients included in the ITT set.

General Considerations

Continuous variables will be described with the number of patients, arithmetic mean, standard deviation, median, minimum, and maximum. For categorical variables, the frequency and proportion will be presented. The values such as arithmetic mean, standard deviation, and proportion will be rounded to two decimal places. If the observation value is missing value, it will be treated as a missing value in the analysis.

Baseline Characteristics including demographics

Descriptive statistics will be used to present variables regarding demographics and disease/medication related data. Continuous variables will be described with the number of patients, arithmetic mean, standard deviation, median, minimum and maximum. For categorical variables, the frequency and proportion will be presented. The values such as arithmetic mean, standard deviation, and proportion will be rounded to two decimal places.

If the observation value is missing value, it will be treated as a missing value in the analysis. Statistical analyses will be performed using SAS V9.2 or higher.

Primary Endpoint:

The frequency of EAMs of interest at baseline: peripheral arthritis, enthesitis and dactylitis

-The frequency and the proportion of patients who are having peripheral arthritis, enthesitis or dactylitis in Korean AS patients at baseline will be presented, and 95% confidence intervals will be calculated.

Secondary Endpoints:

- The percentage of patients with 50% improvement of baseline BASDAI (BASDAI 50) at week 12, 28, 36, and 52
 - The frequency and the proportion of patients with 50% improvement of baseline BASDAI at week 12, 28, 36, 52 will be presented.
- The change of MASES (Maastricht Ankylosing Spondylitis Enthesitis Score) from baseline to week 12, 28, 36, and 52 in patients who had enthesitis at baseline
 - The descriptive statistics (the number of patients, mean, standard deviation, median, min, max) for MASES according to study visit and the change from baseline at week 12, 28, 36, 52 will be presented.

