- The percentage of patients who have enthesitis of the plantar fascia from baseline to week 12, 28, 36 and 52.
 - The frequency and the proportion of patients who have enthesitis of the plantar fascia at week 12, 28, 36, 52 will be presented.
- The change of dactylitis score from baseline to week 12, 28, 36 and 52 in patients who had dactylitis at baseline.
 - The descriptive statistics (the number of patients, mean, standard deviation, median, min, max) for dactylitis score according to study visit and the change from baseline at week 12, 28, 36, 52 will be presented.
- The change of tender and swollen joint counts (TJC, 0-46; SJC, 0-44) from baseline to week 12, 28, 36 and 52 in patients who had peripheral arthritis (≥ 1 swollen joint) at baseline.
 - The descriptive statistics (the number of patients, mean, standard deviation, median, min, max) for tender and swollen joint counts (TJC, 0-46; SJC, 0-44) according to study visit and the change from baseline at week 12, 28, 36, 52 will be presented.

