Annex 1.

1) Maastricht Ankylosing Spondylitis Enthesitis Score (MASES)

MAASTRICHT ANKYLOSING SPONDYLITIS ENTHESITIS SCORE				JE
The MASES and Additional Enthesitis score should only be completed for patients with Enthesitis at the screening visit. Please grade each enthesis below 0(absent), 1(present)				
		Patient Right		Patient Left
1st Costochondral joint		 0	 1	 0  1
7th Costochondral joint		 0	 1	 0  1
Posterior Superior Iliac Spine		 0	 1	 0  1
Anterior Superior Iliac Spine		 0	 1	 0  1
Iliac Crest		 0	 1	 0  1
Proximal Insertion of Achilles tendon		 0	 1	 0  1
Patient Midline				
5th Lumbar Spinous process		 0		 1
Total				
ADDITIONAL ENTHESITIS SCORE				JE
		Patient Right		Patient Left
Fascia plantaris		 0	 1	 0  1

2) Joint Evaluation

JOINT EVALUATION		JE					
Joint (circle the correct answer)		0=Absent		1=Present			
		Pain/Tenderness		Swollen			
		R	L	R	L	R	L
1. Sternoclavicular		0	1	0	1	0	1
2. Acromio-clavicular		0	1	0	1	0	1
3. Shoulder		0	1	0	1	0	1
4. Elbow		0	1	0	1	0	1
5. Wrist		0	1	0	1	0	1
6. Metacarpophalangeal I		0	1	0	1	0	1
7. Metacarpophalangeal II		0	1	0	1	0	1
8. Metacarpophalangeal III		0	1	0	1	0	1
9. Metacarpophalangeal IV		0	1	0	1	0	1
10. Metacarpophalangeal V		0	1	0	1	0	1
11. Thumb Interphalangeal		0	1	0	1	0	1
12. Proximal Interphalangeal II		0	1	0	1	0	1
13. Proximal Interphalangeal III		0	1	0	1	0	1
14. Proximal Interphalangeal IV		0	1	0	1	0	1
15. Proximal Interphalangeal V		0	1	0	1	0	1
16. Hip		0	1	0	1	N/A	
17. Knee		0	1	0	1	0	1
18. Ankle		0	1	0	1	0	1
19. Metatarsophalangeal I		0	1	0	1	0	1
20. Metatarsophalangeal II		0	1	0	1	0	1
21. Metatarsophalangeal III		0	1	0	1	0	1
22. Metatarsophalangeal IV		0	1	0	1	0	1

[figure not shown]
Adalimumab
P15-238 Protocol
Version 2.0

23. Metatarsophalangeal V	0	1	0	1	0	1	0	1

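### The primary objective is worded as EAM frequency on adalimumab, but its only endpoint is measured before the first dose, and the Annex 1 form rule would miss new enthesitis on treatment

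*Combined protocol and SAP*

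**What the plan says.** The primary objective in 8.0 is "To investigate the frequency of EAMs in AS patients on adalimumab therapy in routine clinical practice". The title and the rationale in 7.2 also describe patients who are receiving adalimumab. The research question in 8.0 is broader: it asks about AS patients in Korea, with no treatment condition.

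The primary endpoint in 9.1 is "The frequency of EAMs of interest at baseline: peripheral arthritis, enthesitis and dactylitis". On timing, the same section states: "The baseline assessment should be performed prior to the first dose of adalimumab (Visit1". The primary analysis in 9.7 matches that endpoint, reporting patients "having peripheral arthritis, enthesitis or dactylitis in Korean AS patients at baseline will be presented, and 95% confidence intervals will be calculated".

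For on-treatment visits, 9.7 plans one EAM frequency: "The frequency and the proportion of patients who have enthesitis of the plantar fascia at week 12, 28, 36, 52 will be presented". The other EAM endpoints are changes among patients who had that EAM at baseline, for example "The change of dactylitis score from baseline to week 12, 28, 36 and 52 in patients who had dactylitis at baseline". MASES and the joint counts are handled in the same way.

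Section 9.3 lists MASES, plantar-fascia enthesitis, joint counts and dactylitic digits at weeks 12, 28, 36 and 52, without limiting them to any subgroup. The form in Annex 1 does set a limit: "The MASES and Additional Enthesitis score should only be completed for patients with Enthesitis at the screening visit".

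**The concern.** The objective and its only endpoint appear to name different time points. At Visit 1 no patient has yet received the study-period adalimumab, so the primary estimate is a pre-treatment prevalence. The difference matters on the protocol's own premise, because 7.1 cites cohort evidence that adalimumab reduces enthesitis and peripheral arthritis. Frequencies before and during treatment should therefore be expected to differ.

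Two things are at stake. The first is reporting: the title, objective and rationale are likely to frame the study report, and 9.9 lists no limitations that would correct a misreading. The second is data. Wording can be repaired at any time, but an enthesitis form that was not completed at a follow-up visit cannot be recovered.

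**Working it through.** **1. Objective, endpoint and analysis side by side**

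| Element | Place | Time point |
|---|---|---|
| Title, rationale, primary objective | Title page, 7.2, 8.0 | Worded as on adalimumab |
| Research question | 8.0 | None stated |
| Primary endpoint | 9.1 | Baseline, before first dose |
| Primary analysis | 9.7 | Baseline, with 95% CI |
| Plantar-fascia enthesitis, proportion | 9.7 | Weeks 12, 28, 36, 52 |
| MASES, dactylitis and joint-count changes | 9.7 | Same weeks, baseline-positive patients only |

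No row gives the frequency of peripheral arthritis, dactylitis or overall enthesitis during treatment. Because the change scores are restricted to patients affected at baseline, they cannot show an EAM that first appears on treatment.

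**2. Population.** Section 9.2.1 admits adults with BASDAI of at least 4 despite at least 2 NSAIDs who are eligible for adalimumab. That is narrower than the population in the research question.

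**3. Annex 1 against 9.3.** Section 9.3 defines enthesitis as at least one inflamed site on MASES or at the plantar fascia, and lists both assessments at every follow-up visit. Annex 1 restricts both to patients with enthesitis at screening. The restriction is compatible with the MASES change endpoint, which uses only patients with enthesitis at baseline. It is not compatible with the plantar-fascia percentage, which has no such restriction: a patient who first develops plantar-fascia enthesitis at week 12 would have no form.

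**4. The plan's sample size (9.5).** Inputs: 95% confidence, full width 15 points (half-width 0.075), expected 70% peripheral arthritis and 53% enthesitis. Formula: n = 1.96² × p(1 − p) / 0.075².

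- p = 0.70: 3.8415 × 0.21 / 0.005625 = 143.4, so 144.
- p = 0.53: 3.8415 × 0.2491 / 0.005625 = 170.1, so 171.

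Both reproduce. They size a single proportion, and the only primary proportion in the plan is the pre-dose one. With 200 baseline assessments the full widths, 2 × 1.96 × √(p(1 − p)/200), are 12.7 points (p = 0.70) and 13.8 points (p = 0.53). Rewording the objective changes none of these figures.

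**5. Precision of an on-treatment frequency.** Applying the plan's 20% drop-out to 200 leaves 200 × 0.80 = 160 at week 52. The documents give no on-treatment frequency, so I assume 10% to 50%. Full width = 2 × 1.96 × √(p(1 − p)/160): 9.3 points at 10%, 15.5 points at 50%. That is adequate for a descriptive table.

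**6. Illustration of the gap between the two time points.** Start from the plan's 53% for enthesitis, and assume that 30%, 50% or 70% of cases clear and no new ones arise. These rates are my assumption.

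- 0.53 × 0.70 = 37.1%, a gap of 15.9 points.
- 0.53 × 0.50 = 26.5%, a gap of 26.5 points.
- 0.53 × 0.30 = 15.9%, a gap of 37.1 points.

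**The case against.** The strongest reply is that the on-therapy phrase names the population, not the time of assessment. Section 9.1 describes a study in patients treated with the drug, and the prescription precedes the offer to take part. Section 9.7 adds: "The ITT set will consist of those patients who have received at least one adalimumab treatment and have assessed EAMs at baseline". The research question separates frequency from effectiveness, which maps neatly onto a baseline primary endpoint and on-treatment secondary endpoints. On this reading the endpoint answers the intended question and the fault is one of wording. I accept that the reading is available, and perhaps natural. The protocol never states it, however, so the title, objective and rationale still need aligning.

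Three further objections also have force.

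- Both the endpoint and the analysis text label the result as baseline. A reader might infer that the plan is bound to report a mislabelled figure. The documents do not support that; mislabelling is a risk, not a certainty.
- Change scores in affected patients are a legitimate way to study effectiveness on EAMs, so on-treatment frequencies add to the planned secondary analyses and do not replace them.
- On-treatment proportions of every ITT patient cannot be observed. Under 9.2.2, stopping adalimumab means drop-out, after which only the reason and serious adverse events are collected. Any such table must use patients assessed at the visit.

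What survives is the unaligned wording, the missing on-treatment frequencies for most EAMs, and the contradiction between Annex 1 and 9.3. The Annex 1 contradiction does not depend on how the objective is read.

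**Conclusion.** The point holds as a mismatch of wording with a practical consequence for data capture. Taken literally, the primary objective has no corresponding analysis. Taken as a population label, it is answered, but in terms that invite a pre-dose prevalence to be quoted as an on-therapy one. Separately, the Annex 1 restriction contradicts 9.3 and, if followed, would lose new enthesitis, including from the plantar-fascia percentage that is already planned.

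A reader might infer from the 16 to 37 point range that the primary estimate is wrong by that amount. It is not. The baseline estimate is unaffected, and 144 and 171 stand. The range only shows how far apart the two quantities could lie under assumed clearance of 30% to 70% with no new cases, and it would become an error only if the baseline figure were presented as on-treatment. Nor do the documents support calling this a failure of the design, because the baseline endpoint, its analysis and its sample size agree with one another.

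**What to change.** 1. Restate the title, research question and primary objective as EAM frequency immediately before the first dose, in Korean patients with active AS (BASDAI of at least 4 despite at least 2 NSAIDs) who are starting adalimumab. Align the rationale in 7.2. No sample-size figure changes.
2. Add to 9.7 a secondary, descriptive table: number, proportion and 95% CI of patients with each EAM, by the 9.3 definitions, at weeks 12, 28, 36 and 52. The denominator is the ITT patients assessed at that visit, with the number missing shown beside it. State that the table describes patients still on treatment, since data stop at drop-out. Joint and digit counts are already scheduled at each of these visits.
3. Delete the Annex 1 restriction so that the enthesitis form is completed for all patients at every visit, as 9.3 already lists. Where the form was not completed under the existing rule, report the assessment as missing, not as absence of enthesitis.

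The cost is a protocol wording change, one extra table and slightly more form completion. Item 1 alone removes the mismatch between objective and endpoint. Item 3 is the time-sensitive one, because assessments not recorded cannot be reconstructed.
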